**Admission and Morphine Stabilization:** Once eligibility is determined, participants will be admitted into the secure NYSPI inpatient unit for the duration of the study (approximately 4 weeks). Following admission, participants will begin 5-14 days of stabilization on oral morphine (30 mg, QID: 700, 1300, 1800, 2200 hrs). Additionally, 10-20mg PO hydromorphone doses will be available PRN to address withdrawal symptoms insufficiently managed by oral morphine and supplemental medications alone (to a maximum of 80 mg per day). Hydromorphone will be available in addition to QID oral morphine when deemed clinically appropriate by the study physician. **The participant must exhibit at least "mild" opioid withdrawal according to the COWS (score >8).** Once stabilized, participants will receive oral morphine daily (30 mg) at 700, 1300, 1800, and 2200 hrs. **Prior to the initiation of testing sessions, stability on morphine will be established. Stability will be defined as participants exhibiting a mean COWS score not exceeding 5, with no hydromorphone administration.** Vitals and Respiratory Rate will be assessed immediately before and for one hour (in 15-minute intervals) following the additional dose to ensure against oversedation.

Common clinically used medications such as, clonidine, zolpidem, and Compazine will be available, along with methocarbamol (750-1500 mg, every 6 hours, not exceeding 6000mg in 24 hours). The use of these medications will be suspended by 6 PM the day before a lab session. Participants who cannot stabilize and will be discharged and offered the same end-of-study treatment options described below.

**Safety Session:** Testing will not begin until withdrawal symptoms are no longer present, based upon the Clinical Opioid Withdrawal Scale (COWS: Handelsman et al., 1987). Prior to testing vaped marijuana in combination with intranasal (IN) naloxone, participants will complete a Safety Session. During the safety session, they will receive a test dose of vaped marijuana (25 mg). If a participant's vital signs exceed any of the following benchmarks outlined in the Criteria for Early Discontinuation, they will be discontinued from the trial (Table 1).

Table 1: Study Design														
Week 1							Week 2							
	Mon	Tue	Wed	Thu	Fri	Sat	Sun	Mon	Tue	Wed	Thu	Fri	Sat	Sun

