	Admission	Stabilization	Stabilization	Stabilization	Stabilization	Stabilization	Stabilization	Stabilization	Stabilization	Stabilization	NLX 0mg + V-MJ 0mg	NLX 4mg + V-MJ 25mg		
Week 3							Week 4							
	NLX 0mg + V-MJ 12.5mg	NLX 0mg + V-MJ 25mg	NLX 4mg + V-MJ 12.5mg	NLX 4mg + V-MJ 0 mg			Discharge							

**Laboratory Testing:** Laboratory testing sessions will consist of a modified naloxone challenge procedure (A.K.A. Wang Test: Wang et al., 1974). The challenge begins with baseline assessments. Ten common symptoms of opioid withdrawal (gooseflesh, vomiting, tremor, sweating, restlessness, lacrimation/nasal congestion, yawning, warming/cooling sensations, stomach pain, and muscle ache) will be assessed by a research assistant trained in administering the SOWS/COWS. For safety, the physician or nurse who is providing medical oversight will directly observe its administration.

Each symptom is coded as either “absent” or “present,” with between 1 and 6 points added when a symptom is observed (Table 2). Following pre-test assessments, a physician or nurse practitioner will administer the study drug combination (1000-1100 hrs). Assessments of withdrawal are made at 10-minute intervals for 50 minutes. The total withdrawal score is calculated at the end of the session. To minimize carry-over effects, sessions will be conducted at least 48 hours apart (>5 half-lives of both medications). See Table 1 for an example dosing schedule. The following dose combinations of vaped marijuana (V-MJ) and IN naloxone will be tested in random order:

- Naloxone 0 mg + V-MJ 0.0 mg
- Naloxone 0 mg + V-MJ 12.5 mg
- Naloxone 0 mg + V-MJ 25 mg
- Naloxone 4 mg + V-MJ 0.0 mg
- Naloxone 4 mg + V-MJ 12.5 mg
- Naloxone 4 mg + V-MJ 25 mg

Signs and Symptoms	Table 2: Rating Scale for Opioid Withdrawal											
	(Pre-test)		Time after first naloxone dose									
	0 min		10 min		20 min		30 min		40 min		50 min	
Signs and Symptoms	Present	Absent	Present	Absent	Present	Absent	Present	Absent	Present	Absent	Present	Absent
Gooseflesh	6	0	3	0	3	0	2	0	1	0	1	0
Vomiting	6	0	3	0	3	0	2	0	1	0	1	0
Tremor	6	0	3	0	3	0	2	0	1	0	1	0
Sweating	6	0	3	0	3	0	2	0	1	0	1	0
Restlessness	4	0	2	0	2	0	1	0	1	0	1	0
Lacrimation/ Nasal Congestion	4	0	2	0	2	0	1	0	1	0	1	0
Yawning	4	0	2	0	2	0	1	0	1	0	1	0
Feeling of Change in Temperature	3	0	1	0	1	0	1	0	1	0	1	0
Stomach Pain	3	0	1	0	1	0	1	0	1	0	1	0
Muscle Ache	3	0	1	0	1	0	1	0	1	0	1	0
Actual time of observation												
Scores												
Pupil Diameter												

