STATISTICAL ANALYSES

Data Analysis Plan: The distributions of all continuous variables will be checked for normality, and transformations will be employed (if necessary) before applying specific parametric techniques. Before performing specific analyses, we will examine all outcomes for outliers. All statistical comparisons will be two-sided and the critical level for rejection of the null hypothesis will be considered to be a p-value of < 0.05 . Where needed, False Discovery Rate Analysis will be used to adjust critical p values to control for multiple comparisons. Any comparison where homogeneity is violated will not be considered significant. Means, standard deviations, proportions, and 95% confidence intervals will be used to describe all continuous variables.

Dropouts and Missing Data: As this is an inpatient laboratory study within a controlled setting, we expect only minimal intermittent missing data, though we do expect to have some subjects drop out without completing all of the experimental conditions. We will use all available data from subjects prior to drop-out. We will account for missing data directly using mixed-effects models (MEM) (Diggle et al. 2002). MEMs do not require complete measurements to estimate effects and inferences are valid provided that data are “missing at random” (Little & Rubin, 2002). ‘Missing at random’ (i.e. the missing mechanism does not depend on the value of the unobserved outcome) is un-testable in most medical research and in our study as well. One can assume either parametric or semi-parametric models for the missingness that does depend on the unobserved outcome value and do the analysis (Diggle and Kenward 1994, Kenward 1998). Comparison of the inferences from assuming various models for the missingness provides a measure of the validity of the efficacy estimate from the model that assumes missing ‘at random’. One can also compute a local sensitivity index which measures the change in the estimated treatment effect in a neighborhood of the ‘missing at random’ model for missingness (Rotnitzky et al. 1998). We will perform sensitivity analyses based on these two approaches to assess the effect of the assumption of missing ‘at random’ on the inference.

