Randomization: Once a participant is enrolled, a randomization sequence table will be generated by a blinded statistician. The table will determine the order of testing of the various dose combinations of dronabinol (.00, .35, and .70 mg), and naloxone (0.0, 0.2 and 0.4 mg).

Aims, Outcome Measures, and Hypotheses

Primary Aim: Assess the ability of inhaled dronabinol to alter the severity of naloxone-precipitated withdrawal.

- The primary dependent variable (DV) for this aim will be the total opioid withdrawal score from the testing session. Repeated-measures analysis of variance (ANOVA) will be used to assess differences among the various dose conditions.
- We hypothesize that there will be a dose-dependent effect of dronabinol to attenuate the severity of naloxone-precipitated withdrawal.

Secondary Aim: Assess the safety of inhaled dronabinol in combination with naloxone.

- The primary DVs are the SAFTEE (AEs not related to withdrawal) and physiological parameters. Generalized mixed-effects models with participant as a random effect and an autoregressive correlation structure for the within-participant observations will be used to analyze the total number of AEs and their severity.
- We hypothesize that dronabinol, in combination with naloxone, will produce more AEs than placebo but less than naloxone alone.

Secondary Aim: Assess the impact of inhaled dronabinol on naloxone's effects on pupil diameter (i.e., μ -opioid receptor blockage).

- The primary DV will be pre-to-post- medication change in pupil diameter from each testing session. Repeated-measures ANOVA will be used to assess differences among the various dose conditions.
- We hypothesize that dronabinol will not significantly alter naloxone's effects on pupil diameter (in comparison to placebo).

Secondary Aim: Assess the abuse potential of inhaled dronabinol.

- The primary DV will be pre-to-post- medication change in positive subjective drug ratings such as drug "Liking" and "Good Effect."
- We hypothesize that self-reported dronabinol "Liking" will not be significantly greater than placebo.

Power

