To approximate a suitable number of subjects for a traditional hypothesis-testing approach, a power analysis was conducted using G* Power 3.1.7. Estimates of the magnitude of the medication effect on withdrawal were estimated using a previous study that assessed naloxone-precipitated withdrawal (Jones et al., 2016). Based on these data we calculated a Cohen's D effect size of .75, which constituted a 15-point difference (mean SD of 20) in total withdrawal score (0-125) between any two dose conditions. Applying this to the current proposal, a total sample size of 16 completers should provide 90% power to detect this difference at a p of < 0.05 . Sixteen completers will provide 88% power to detect a 10-mm difference in positive subjective effects, e.g. "Liking" on a 100-mm VAS scale (alpha of 0.05). This analysis assumes a SD of 12 mm and a Cohen's D effect size of 0.84 based on previous visual analog scale assessments of abuse liability of opioids and cannabinoids (Cooper et al., 2018, Jones et al., 2017).

Due to the exploratory nature of this study, effect size estimates will be the main research outcome for the secondary aims, along with the interpretation of confidence interval lengths and degree of overlap to indicate precision and degree of difference (i.e., threshold of clinical importance) between dose conditions (respectively). A sample size of 16 completers was determined to be sufficient to obtain precise 95% confidence intervals with a margin of error of at most 25%. Thus, with regard to the detection of differences in all the study aims, these calculations suggest that this study is suitably powered.

Sex as a Biological Variable

Sex-specific comparisons will be performed to provide an indicator of a Sex x Treatment interaction. The within-subject nature of the study's design should control for potential sex differences. Though not powered to specifically detect sex differences, we are still in compliance with NIH policies to enroll males and females. Furthermore, sex as a biological variable will be examined and reported in accordance with NIH policy (https://orwh.od.nih.gov/sites/orwh/files/docs/NOT-OD-15-102_Guidance.pdf).

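### The primary ANOVA leaves its contrasts and error term open; pooling error over naloxone 0 mg and 4 mg sessions would give the V-MJ contrasts wrong standard errors

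*SAP*

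**What the plan says.** The SAP, under Aims, Outcome Measures, and Hypotheses, sets the primary outcome: "The primary dependent variable (DV) for this aim will be the total opioid withdrawal score from the testing session". The analysis is one sentence: "Repeated-measures analysis of variance (ANOVA) will be used to assess differences among the various dose conditions". It does not say whether the layout is six levels of one factor or naloxone by V-MJ, which contrast is primary, which error term a contrast uses, or what happens if sphericity fails.

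The Data Analysis Plan adds three general rules: "All statistical comparisons will be two-sided"; "the critical level for rejection of the null hypothesis will be considered to be a p-value of < 0.05"; and "Any comparison where homogeneity is violated will not be considered significant". Under Dropouts and Missing Data, mixed-effects models are named for incomplete data, but no covariance structure is given for the withdrawal score.

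The protocol (Study Procedures, Laboratory Testing) crosses naloxone 0 or 4 mg with V-MJ 0, 12.5 or 25 mg, so three of the six conditions, for example "Naloxone 0 mg + V-MJ 12.5 mg", contain no naloxone. On entry to testing, the Safety Session paragraph states: "Testing will not begin until withdrawal symptoms are no longer present, based upon the Clinical Opioid Withdrawal Scale". The stabilisation rule just before it requires a mean COWS of no more than 5 without hydromorphone.

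The SAP's Power section plans on a Cohen's d of 0.75, "which constituted a 15-point difference (mean SD of 20) in total withdrawal score (0-125) between any two dose conditions". One SD therefore serves every pair of conditions.

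**The concern.** The primary hypothesis is that V-MJ attenuates naloxone-precipitated withdrawal. The contrasts that answer it are V-MJ 25 mg vs 0 mg and 12.5 mg vs 0 mg, both within naloxone 4 mg. Participants who enter testing without withdrawal and receive no naloxone should have low, compressed scores, while the naloxone 4 mg sessions should spread widely.

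A common error term averages these two groups of sessions. It then describes neither: it can be too small or too large for the contrasts that matter, depending on correlations nobody knows in advance, and it is too large for V-MJ contrasts without naloxone. The confidence intervals are wrong along with the p values. A mixed model with only a random participant intercept makes the same assumption, so the missing-data paragraph does not by itself avoid the problem.

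**Working it through.** **Inputs from the documents.** 16 completers; six conditions; two-sided 0.05; SD 20 and a 15-point difference.

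**Assumptions, because the documents give no value.** SD 20 applies to each naloxone 4 mg condition. The naloxone 0 mg SD is 2, 5 or 10. The correlation between naloxone 4 mg sessions is 0.3, 0.5 or 0.7, and between naloxone 0 mg sessions 0.5. The correlation across naloxone levels is 0 or 0.3. Scores are multivariate normal with no V-MJ effect.

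**The plan's own power figure.** For a paired t test with 16 completers, the noncentrality is 0.75 × √16 = 3 on 15 df. Power is 80.1% two-sided and 88.8% one-sided, so the stated 90% is approached only with a one-sided test. That is a separate matter; it is given here because 80% is the baseline once each contrast has its own error.

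**Step 1: expected error terms, worked case.** Take naloxone 0 mg SD 5, correlation 0.5 within each naloxone level, and 0.3 across levels.

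- True SD of a V-MJ difference within naloxone 4 mg: √(2 × 400 × (1 − 0.5)) = 20.
- Six-condition residual mean square = (trace − total/6)/5, where trace is the sum of the variances and total is the sum of all entries of the covariance matrix. Trace = 3 × 400 + 3 × 25 = 1275. Total = 1275 + 6 × 200 + 6 × 12.5 + 18 × 30 = 3090. Mean square = (1275 − 515)/5 = 152 on 75 df. Implied SD of a difference: √(2 × 152) = 17.4, a ratio to truth of 0.87.
- 2x3 layout, V-MJ error pooled over both naloxone levels: (400 × 0.5 + 25 × 0.5)/2 = 106.25 on 60 df. Implied SD: √(2 × 106.25) = 14.6, a ratio of 0.73.
- Error from the naloxone 4 mg sessions only: 400 × 0.5 = 200. Implied SD 20, a ratio of 1.

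**Step 2: what the ratio does to the level.** Ignoring sampling error in the mean square, type I error is about 2 × (1 − Φ(ratio × critical t)). For the six-condition error this is 2 × (1 − Φ(0.87 × 1.99)), about 0.08; simulation gives 0.09. For the 2x3 pooled error it is 2 × (1 − Φ(0.73 × 2.00)), about 0.14.

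**Step 3: simulation over the assumed range.** Type I error for V-MJ 25 mg vs 0 mg within naloxone 4 mg:

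| Error term | Correlation between naloxone 4 mg sessions | Type I error |
|---|---|---|
| Six conditions pooled, 75 df | 0.3 | 0.09–0.13 |
| Six conditions pooled, 75 df | 0.5 | 0.05–0.09 |
| Six conditions pooled, 75 df | 0.7 | 0.02–0.04 |
| 2x3, V-MJ error pooled over naloxone levels, 60 df | 0.3–0.7 | 0.10–0.17 |
| Naloxone 4 mg sessions only | 0.3–0.7 | about 0.05 |

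The six-condition error is conservative at 0.7 and mostly inflated at 0.3 to 0.5. The 2x3 pooled error is inflated in every setting, because it always averages in the smaller naloxone 0 mg variance.

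**Step 4: the homogeneity rule.** Suppose it is applied as a six-condition sphericity test (Mauchly). In the worked case about 100% of trials are flagged, and type I error falls from 0.09 to 0.000. Under a simpler assumption, one common correlation of 0 to 0.7 among all six conditions, a naloxone 0 mg SD of 10 is flagged in 57–78% of trials and power for 15 points falls from 71–98% to 22–35%. With SD 5, power falls from 75–97% to 0%. If the rule is instead applied pair by pair, two naloxone 4 mg conditions with similar variances would not normally be flagged, and the results of Step 3 stand.

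**The case against.** The strongest reply is that the SAP never says a pooled error will be used. The conditions cross two drugs. A factorial within-subject ANOVA with separate error strata, or paired follow-up contrasts, fits the same sentence, and simulated levels for those tests are 0.046 to 0.053. This stands. A reader might infer that the plan commits to one error term and so fails to deliver 0.05; the documents do not support that.

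The factorial reading is not safe throughout, however. Its V-MJ main-effect test holds its level but averages V-MJ over the no-naloxone sessions, which is not the aim. A simple effect within naloxone 4 mg that uses the V-MJ error pooled over both naloxone levels gives 0.10 to 0.17. Only an error specific to naloxone 4 mg is reliable, and the SAP does not specify one.

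Second, the size and direction rest on an SD and correlations that no document gives, and the planning SD of 20 is not tied to the naloxone 4 mg conditions. This also stands. A reader might infer that the flaw favours a false claim for V-MJ. That is not supported: the six-condition error is conservative when naloxone 4 mg sessions correlate strongly, the homogeneity rule may block significance altogether, and two-sided errors fall in either direction.

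Third, the SAP has a False Discovery Rate step. It addresses the number of tests, not the standard error of each, so it is no answer here. All levels above are for a single contrast.

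**Conclusion.** The concern holds as a specification gap with a real consequence. The low spread expected without naloxone is a sound inference from the protocol's entry rule, not a documented figure. Given that inference, two ordinary ways of carrying out the stated ANOVA give the primary V-MJ contrasts wrong standard errors. Under the listed assumptions, type I error at nominal 0.05 runs from about 0.02 to 0.13 for the six-condition error and from about 0.10 to 0.17 for the 2x3 error pooled over naloxone levels. An error term from the naloxone 4 mg sessions alone holds 0.05 throughout. The homogeneity rule is no remedy: on one reading it makes a significant result nearly unobtainable, and on the other it leaves the problem in place. The change should be made, as a low-cost improvement to the analysis.

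**What to change.** In the SAP, under the Primary Aim:

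- Name V-MJ 25 mg vs 0 mg and V-MJ 12.5 mg vs 0 mg, both within naloxone 4 mg, as the primary contrasts.
- Give each an error term from the naloxone 4 mg sessions only: either within-person paired differences, or a mixed model with variances and correlations separate by naloxone level and Kenward-Roger degrees of freedom. The mixed model also uses data from participants who drop out.
- State that the homogeneity rule in the Data Analysis Plan does not apply to these contrasts.
- Use the same approach for pupil diameter, which has the same ANOVA sentence. A difference in spread between naloxone levels is plausible there too, but no document gives a figure.
- Reconcile the dose list under Randomization (three dronabinol by three naloxone levels) with the protocol's six V-MJ and naloxone conditions, so that the contrasts refer to conditions that will be run.

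The cost is SAP wording and some error degrees of freedom. With paired differences these fall from 75 to 15, and the critical t rises from 1.99 to 2.13. Two-sided power for 15 points is then 80% if 20 is the SD of the paired difference.

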**Additional Assessments During Laboratory Sessions (completed at -30, +15, +30, +45, +60):**

- The subjective effects battery will consist of Visual Analog Scales and the Opioid Craving Questionnaire (Tiffany et al., 1993),
- Two cognitive tasks will be used in the proposed studies. The Digit Symbol Substitution Task (McLeod et al., 1982) and the Divided Attention Task assesses attention (DAT; Miller, 1987).
- Brief Psychiatric Rating Scale (BPRS) will be performed at +45

At the end of the test testing session, the participant may receive a rescue dose of oral morphine (30 mg). If COWS scores remain >5 at the next measurement timepoint (+15 minutes) an additional 20 mg may be provided, at the discretion of a study physician. The testing session may also be terminated 20 minutes following naloxone administration (if withdrawal is too severe (COWS >20) and the rescue dose given at this time. A physician, nurse practitioner, or nurse will be notified once the COWS score goes above 9.

The RA will notify the physician/nurse practitioner once the criterion for the morphine rescue has been met, who will then administer the rescue dose. If a morphine rescue is given, vital signs will continue to be monitored for the entire 4-hour period. If a participant receives a rescue dose during the testing session, the 1 pm morphine dose may be held at the discretion of the physician.

Suicidality and Pregnancy will be monitored weekly throughout the inpatient period using the CSSRS and a urine pregnancy test, respectively.

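### Pupil diameter and drug Liking are planned as raw pre-to-post change; using the session baseline as a covariate is expected to narrow the intervals, by an amount the documents do not let us compute

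*SAP*

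**What the plan says.** The SAP, under Aims, Outcome Measures, and Hypotheses, defines two secondary outcomes as raw change.

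- Pupil diameter: "The primary DV will be pre-to-post- medication change in pupil diameter from each testing session". The model follows: "Repeated-measures ANOVA will be used to assess differences among the various dose conditions". No covariate is named.
- Abuse potential: the outcome is "pre-to-post- medication change in positive subjective drug ratings", with Liking as an example. No model is named.

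The SAP's Power section then says that "effect size estimates will be the main research outcome for the secondary aims", to be read together with the length and overlap of confidence intervals.

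The Protocol shows that the baselines are already planned. The visual analog scales fall under "Additional Assessments During Laboratory Sessions (completed at -30, +15, +30, +45, +60" minutes. For pupil diameter, Study Procedures says "Following pre-test assessments, a physician or nurse practitioner will administer the study drug combination", and Table 2 has a pupil row with a pre-test column. The design is a crossover: "The following dose combinations of vaped marijuana (V-MJ) and IN naloxone will be tested in random order", and six combinations are listed.

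**The concern.** Each participant receives every condition, so stable differences between people cancel in the condition contrasts. A session baseline can then help only through its session-to-session deviation from the participant's own level. A change score removes that deviation with a fixed coefficient of 1. If the true within-participant slope of post-dose on pre-dose is not 1, the subtraction leaves avoidable noise in the contrast.

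This matters more here than it usually would. Interval width is itself part of the reported secondary result, and it comes from 16 completers. Both aims also predict the absence of an effect: pupil response to naloxone not significantly altered, and Liking not significantly above placebo. Extra noise makes such predictions easier to satisfy, so imprecision is not the conservative direction.

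**Working it through.** **Inputs from the documents.** 16 completers; six conditions (Protocol, Study Procedures); two-sided alpha 0.05; for Liking a 10-mm difference, SD 12 mm, stated d 0.84 and stated power 88% (SAP, Power).

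**Not in the documents.** The within-participant pre/post correlation r, the ratio k = SDpre/SDpost, and any SD for pupil diameter. All three are treated as unknown. r and k are taken as the same in every condition.

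**Step 1: the plan's own figure.** A two-sided paired t-test with n = 16 (15 df) gives 87.6% power at d = 10/12 = 0.833 and 88.1% at d = 0.84. The stated 88% reproduces. With 12 mm as the SD of the paired difference, the 95% half-width is 2.131 × 12/√16 = 6.4 mm. The SAP does not say whether 12 mm refers to the change, the post-dose score or the paired difference.

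**Step 2: large-sample variances.** With within-participant post-dose variance s²:

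- change score: s²(1 + k² − 2kr)
- post-dose value alone: s²
- baseline-adjusted post-dose value: s²(1 − r²)

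Change minus adjusted is s²[(1 + k² − 2kr) − (1 − r²)] = s²(k − r)², which is never negative and is zero when r = k, that is, when the slope r/k equals 1. Change is worse than ignoring the baseline only when r < k/2.

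**Step 3: interval widths if k = 1.** Width of change relative to adjusted is √[2(1 − r)/(1 − r²)] = √[2/(1 + r)].

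| r | change / adjusted | change-score interval wider by |
|---|---|---|
| 0 | 1.414 | 41% |
| 0.5 | 1.155 | 15% |
| 0.7 | 1.085 | 8% |
| 0.8 | 1.054 | 5% |
| 0.9 | 1.026 | 3% |

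**Step 4: other values of k.** At k = 0.5, r = 0.5 the variance ratio is (1 + 0.25 − 0.5)/(1 − 0.25) = 1, so there is no gain. At k = 0.3, r = 0 it is 1.09, so change is about 4% wider. At k = 0.3, r = 0.3 it is 0.91/0.91 = 1, again no gain.

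**Step 5: small-sample price.** Simulation used 2,000 runs of 16 participants × 6 sessions. Error df in the pooled model are (16 − 1) × (6 − 1) = 75 for change and 74 with one covariate. The table gives adjusted width divided by change width.

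| k | r | pooled model | two conditions only |
|---|---|---|---|
| 1 | 0 | 0.71 | 0.74 |
| 1 | 0.5 | 0.87 | 0.90 |
| 1 | 0.8 | 0.96 | 0.99 |
| 1 | 0.9 | 0.98 | 1.02 |
| 0.5 | 0.5 | 1.007 | 1.04 |
| 0.1 | 0 | 1.00 | 1.04 |
| 0.1 | 0.5 | 0.91 | 0.94 |

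The largest widening in the pooled model was 0.7%. In a two-condition contrast it was about 4%.

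**Step 6: Liking in millimetres.** Taking 12 mm as the SD of the paired difference in change, k = 1 and a two-condition contrast, the 6.4-mm half-width becomes about 4.7, 5.8, 6.1, 6.3 and 6.5 mm at r = 0, 0.5, 0.7, 0.8 and 0.9. Power moves from 88% to about 99, 93, 90, 88 and 87%.

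**The case against.** The strongest reply is that change is a valid analysis. Under randomisation it targets the same condition contrast as the adjusted post-dose value, the aims are declared exploratory, and the one reproducible secondary figure (88% for Liking) holds. This stands: the point concerns precision, not bias or validity.

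The size also rests on two quantities that the documents omit. A reader might infer from the k = 1 row at r = 0 that change scores throw away half the sample, or that they lose to adjustment at every correlation below 1. The documents do not support either. The first needs r = 0 with equal SDs; the second fails at r = k, and at high r the gain is only a few percent. Nor is adjustment free: a degree of freedom is spent, and separate two-condition contrasts can widen slightly.

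Liking is the weaker half. If pre-dose Liking scarcely varies and says little about the post-dose score (an assumption), there is little to gain. Because no model is named for that aim, a covariate is not excluded either.

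For pupil diameter, no equivalence margin is given, so a narrower interval alone would not establish that naloxone's effect is preserved.

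Finally, the pupil baseline could be questioned. Table 2 labels the pre-test column 0 min, while Criteria for Early Discontinuation puts vaping at T −15 and naloxone at T 0. A reading at T 0 would follow vaping. That would compromise the change score as well as the covariate, and the Study Procedures text does place pre-test assessments before the drug combination.

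**Conclusion.** The point holds as a recommended precision improvement. Both outcomes are planned as raw change, no baseline covariate is specified, and the session baselines are already scheduled. In large samples adjustment is never less precise than change, and in a pooled six-condition model the worst simulated loss was 0.7%. The possible gain is much larger: removing an excess width of about 41% to 3% over r = 0 to 0.9 if k = 1. The actual gain is unknown and may be nil if the within-participant slope is close to 1. The case is firmer for pupil diameter than for Liking. Nothing here shows that a planned conclusion would change or that a stated power target would be missed.

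**What to change.** In the SAP, under the pupil-diameter and abuse-potential aims, pre-specify one model per outcome across all six conditions:

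- outcome: the post-dose value, naming the reading or summary used;
- condition as fixed effect and participant as random effect;
- that session's baseline as covariate, split into the participant's mean baseline and the session's deviation from it, so that the within-participant slope is not mixed with the between-participant one;
- report adjusted condition differences with 95% confidence intervals, and keep the change score as description.

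State that the baseline is the reading taken before any study drug, and align Table 2's 0 min label with the T −15 and T 0 timings. Because a session baseline can carry residue from the previous session, also reconcile the stated session spacing (24 hours in the Lay Summary, at least 48 hours in Study Procedures).

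The cost is SAP wording and one or two degrees of freedom. No additional measurement is needed, provided the pre-test pupil reading is taken before vaping. Estimating all contrasts from the pooled model, rather than in separate pairs, keeps the possible widening below 1%.

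### The 90% power stated for the primary outcome does not follow from the SAP's own inputs: 16 completers at d = 0.75 give 80% with a two-sided 0.05 test

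*SAP*

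**What the plan says.** The Data Analysis Plan in the SAP fixes the testing convention: "All statistical comparisons will be two-sided". Significance is judged at the 5% level. The plan also provides for multiplicity, if the need arises: "False Discovery Rate Analysis will be used to adjust critical p values to control for multiple comparisons".

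The Power section names G*Power 3.1.7 and an earlier study of naloxone-precipitated withdrawal. From those data "we calculated a Cohen's D effect size of .75", described as "a 15-point difference (mean SD of 20) in total withdrawal score (0-125) between any two dose conditions". It then concludes that "a total sample size of 16 completers should provide 90% power to detect this difference at a p of < 0.05".

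The next sentence covers the visual analog scale ratings: "Sixteen completers will provide 88% power to detect a 10-mm difference in positive subjective effects", again at alpha 0.05, with SD 12 mm and d = 0.84. The section closes by saying that the study is suitably powered with regard to all its aims.

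The SAP does not name the test family, the sidedness or the within-subject correlation used for either calculation. The design is a within-subject crossover, so 16 completers means 16 pairs for any comparison of two conditions.

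**The concern.** Two power figures stand side by side with the same n and the same alpha, and the smaller effect (0.75) carries the higher power (90% against 88% for 0.84). Under a single convention that is impossible, because power rises with effect size.

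The 90% is the only power justification for the primary aim. If the true figure is 80%, the chance of missing a real 15-point reduction is about 1 in 5, not 1 in 10. A non-significant primary result would then be given more weight as evidence of no effect than the design supports. The closing claim about all aims rests partly on this figure.

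**Working it through.** **Inputs (SAP, Power and Data Analysis Plan).** n = 16 pairs; difference 15 points; SD 20; d = 15/20 = 0.75; alpha 0.05; two-sided. Companion figure: difference 10 mm; SD 12 mm; stated d = 0.84 (10/12 = 0.833).

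**Formula.** For a paired t-test, the noncentrality is d × √n with n − 1 degrees of freedom. Power is the probability that a noncentral t variable falls beyond the critical value. With df = 15 the critical value is 2.131 two-sided and 1.753 one-sided.

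**Step 1: try to reproduce the 90%.** Noncentrality = 0.75 × √16 = 3.0.

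| Test, n = 16, d = 0.75 | Power |
|---|---|
| Paired t, two-sided 0.05 | 80.1% |
| Paired t, one-sided 0.05 | 88.8% |

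The two-sided test that the SAP prescribes falls about 10 points short. The one-sided test comes close to 90%, so a one-sided setting in the software is a plausible source, though nothing in the documents proves it.

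**Step 2: find the convention from the companion figure.** Noncentrality = 0.84 × 4 = 3.36.

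| Test, n = 16 | Power |
|---|---|
| d = 0.84, two-sided | 88.1% |
| d = 0.833, two-sided | 87.6% |
| d = 0.84, one-sided | 94.0% |

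The stated 88% is a two-sided paired t-test. Under that convention the primary figure is 80%.

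**Step 3: what 90% two-sided would take.**
- At d = 0.75: 20 completers give 88.9% and 21 give 90.5%, so 21 are needed.
- At n = 16: d = 0.868, which at SD 20 is 0.868 × 20 = 17.4 points.

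**Step 4: the other reading of SD 20.** If 20 is the SD within each condition and r is the within-subject correlation, the SD of the paired difference is 20 × √(2(1 − r)) and the paired effect size is 0.75/√(2(1 − r)).

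| r (assumed) | Paired effect size | Two-sided power |
|---|---|---|
| 0 | 0.530 | 51% |
| 0.3 | 0.634 | 66% |
| 0.5 | 0.750 | 80% |
| 0.6 | 0.839 | 88% |
| 0.7 | 0.968 | 95% |

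Reaching 90% requires r = 1 − (0.75/0.868)²/2 ≈ 0.63. At r = 0.5 the two readings coincide.

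**Step 5: repeated-measures ANOVA, the named primary analysis.** Take noncentrality λ = n·m·f²/(1 − r) for m levels, and assume r = 0.5.
- m = 2, f = 0.75/2 = 0.375: λ = 16 × 2 × 0.1406/0.5 = 9.0, power 80.1%, the same as the paired test.
- m = 3, f = 0.375: λ = 13.5, power 88.8%. But f = d/2 is the two-level conversion. With three means spanning 0.75 SD, f can be at most 0.75 × √8/6 = 0.354 (λ = 12.0, power 84.7%).
- m = 3 with the middle mean halfway, the smallest f for that span: f = 0.75/√6 = 0.306, λ = 9.0, power 72.5%.

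**Step 6: multiplicity.** The power statement makes no allowance for the false discovery rate adjustment. As an illustration only, alpha 0.025 (two active-dose contrasts, worst case) gives 69%.

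**The case against.** The strongest reply is that the documents do not fix the value at 80%. A mean SD reads naturally as an average of condition SDs, and then power depends on an unstated correlation. A within-subject correlation of 0.63 or more is possible, and it would give 90% or better. The primary analysis is also a repeated-measures ANOVA, and a three-level calculation with f = 0.375 and r = 0.5 returns 88.8% without any one-sided test. The two power figures concern different outcomes, with effect sizes from different earlier studies, so they conflict only if the same test and the same SD definition underlie both. Finally, 80% is a conventional level for a proof-of-concept study, the secondary aims rest mainly on estimation, and no conduct or risk changes.

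Part of this stands. The source of the 90% is unproven, and 80% holds on the reading that 0.75 is the paired effect size. The secondary aims do not depend on this figure alone, and the 69% in the multiplicity illustration is not the SAP's own procedure.

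The rest does not rescue the text. The SAP states no correlation, no f and no number of levels. It frames the target as a contrast of two conditions, which is a pairwise comparison. The ANOVA route needs an f larger than a 15-point span over three doses can produce. The one figure in the section that can be verified was computed as a two-sided paired test. If a favourable correlation was used, it has to be written down, so a correction is needed on either reading.

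**Conclusion.** The concern holds. Under the SAP's own two-sided 0.05 rule, 16 completers with d = 0.75 have 80.1% power, not 90%, so the type II error is about double the stated one. This takes 0.75 as the paired effect size (SD of within-subject differences 20), the reading under which the companion 88% reproduces. If 20 is a condition SD, power runs from 66% at r = 0.3 to 95% at r = 0.7, and 90% depends on a correlation of about 0.63 that the SAP does not give. The design is not invalidated, since 80% is a usual target. What is wrong is the operating characteristic quoted for the primary outcome.

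**What to change.** First check the original G*Power inputs: test family, number of tails, and what the SD of 20 describes. Then keep N = 16 and correct the Power section.

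- If 20 is the SD of paired differences, suggested wording is: *Sixteen completers give 80% power (two-sided alpha 0.05, paired comparison, SD of within-subject differences 20) to detect a 15-point difference; 90% power corresponds to 17.4 points.*
- If 20 is a condition SD, state the assumed within-subject correlation and its source, and give the power that follows, with a range of correlations around it.
- State whether the figure allows for the false discovery rate adjustment.
- Revise the closing sentence on all aims to match.

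The cost is SAP wording only. No extra participants are needed; the stated power becomes less favourable.
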